# 2.2.2 Randomization and Blinding

The study will consist of 2 parts. Part 1 is open-label and non-randomized. Based on feedback from study Investigators in Part 1 regarding maneuverability and ease of use of the LYR-220-16 matrix, the Sponsor decided to drop this treatment arm in Part 2 of the study.

Approximately 40 subjects who complete the study Screening assessments and the run-in period, and meet all eligibility criteria on Day 1 in the Part 2 of the study will, before any treatment, be randomized in a 1:1 ratio to 1 of the 2 study arms:

- Treatment Arm A: bilateral insertion of LYR-220-32 (7500 μg)
- Treatment Arm B: bilateral sham treatment control

Subjects will be stratified for treatment assignment according to the following criteria:

Nasal polyps (Yes vs No)

No more than 10 subjects with nasal polyps will be randomized in each treatment arm. Treatment will be assigned according to a randomization scheme generated by the Sponsor or designee. Randomization will be conducted using Interactive Response Technology (IRT).

Subjects should remain blinded to their treatment assignment until the final study database is locked. To maintain subject blinding (LYR-220 or sham) in Part 2 of the study, each subject will wear an eye mask (i.e., blindfold) and ear/headphones at the time of the LYR-220 administration/sham procedure and at all post Day 1 visits (scheduled or unscheduled) during any endoscopy assessments and during the LYR-220 administration/sham removal procedure.

Breaking the blind is expressly forbidden except in the event of spontaneous dislodgment of LYR-220, or a medical emergency where the identity of the treatment assignment must be known in order to properly treat the subject. If breaking the blind is required because of a medical emergency, decision to unblind lies solely with the investigator.

In all cases where the code is broken, the investigator must record the date and reason for code breaking.

A Sponsor blind was implemented in Part 2 of the study, as outlined in the Study Blinding Plan.

## 2.2.3 Investigational Product

The LYR-220 System is a combination product comprised of a single-use applicator, preloaded with an anti-inflammatory drug matrix. The LYR-220 drug matrix contains mometasone furoate (MF), an active ingredient in multiple FDA-approved products indicated for therapeutic and prophylactic management of seasonal and perennial allergic rhinitis (AR), nasal polyps, a phenotype of CRS disease, as well as asthma. The LYR-220 drug matrix is designed to gradually soften over time and is made of bioabsorbable polymers that have been used as components of approved pharmaceutical drugs and/or medical devices.

LYR-220 has a tubular braid configuration with a uniform diamond pattern throughout. It is designed to be self-retaining against the mucosal tissues to allow effective drug transfer for up to 24 weeks. The matrix is comprised of a base structure and a drug formulation layer. The base structure is composed of poly(L-lactide-co-glycolide) and poly(L-lactide-co-ε-caprolactone) elastomer to provide a 3-dimensional structure and elasticity. The drug formulation layer

consists of the active ingredient, MF, embedded in the inactive ingredients containing poly(L-lactide-co-ε-caprolactone) and poly(L-lactide) to control the release rate of MF. Two designs of LYR-220, LYR-220-32 drug matrix and LYR-220-16 drug matrix, manufactured with 32 and 16 woven fibers, respectively, will be assessed in this study. Both designs have the same nominal dimensions of 20 mm in diameter and 16 mm in length in the unconstrained state.

Each LYR-220 drug matrix contains 7500  $\mu$ g MF. LYR-220 is intended to be administered bilaterally into the ethmoid cavity, in which ethmoid sinuses have been removed previously by a bilateral ethmoidectomy, by an otolaryngologist under endoscopic visualization using the provided single-use applicator. Once administered, each LYR-220 is designed to gradually deliver sustained doses of MF to the inflamed mucosal tissue over a 24-week resident time. Bilateral placement of LYR-220 (7500  $\mu$ g) is designed to deliver a total dose of 15,000  $\mu$ g MF over the 24 weeks, or an average daily dose of 89  $\mu$ g MF per person (or 45  $\mu$ g MF per nostril).

#### 2.2.4 Discontinuation of Study Subjects

Subjects will be encouraged to complete the study through the post-treatment follow-up period. Each subject is free to discontinue from the study at any time, for any reason, and without penalty or loss of benefit. Participation in the study treatment may be discontinued for any of the following reasons:

- Occurrence of any medical condition or circumstance that exposes the subject to substantial risk and/or does not allow the subject to adhere to the requirements of the protocol, including early removal of LYR-220.
- Any serious adverse event, clinically significant adverse event, severe laboratory abnormality, intercurrent illness, or other medical condition that indicates to the Investigator that continued participation is not in the best interest of the subject.
- Subject's decision to withdraw.
- Requiring sinonasal surgery as rescue treatment.
- If deviations to the use of prohibited medications occur during run-in or study treatment periods, the Investigator, in consultation with the Sponsor and Sponsor's medical monitor will decide on a case-by-case basis whether the subject may continue in the study based on the time the prohibited medication was administered and its pharmacology.
- Subject's failure to comply with protocol requirements or study related procedures.
- Termination of the study by the Sponsor or a regulatory authority that has provided approval to proceed.

Subjects who withdraw or are withdrawn from the study treatment will be requested to return to the clinic for the assessments and procedures scheduled for the EOT and EOS visits.

#### 2.2.5 Sample Size Determination

Because the primary objective of this study is to assess the safety, tolerability, and pharmacokinetics of LYR-220, the sample size determination is not based on statistical power considerations. Up to 10 subjects will be treated in the Part 1 and approximately 40 subjects will be treated in Part 2 of the study, respectively.

# 2.3 Study Endpoints

#### 2.3.1 Primary Endpoint

The primary endpoint is product-related treatment-emergent serious adverse events (TESAEs).

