3. STUDY OBJECTIVES AND ENDPOINTS

The study objectives and endpoints are:

Study Objectives	Study Endpoints
Primary	
To evaluate unexpected serious adverse events related to LYR-220	- Product-related unexpected serious adverse events
Pharmacokinetics	
To evaluate the pharmacokinetics of LYR-220	 Plasma MF concentrations at 1 hour (±10 minutes) post study treatment administration and at Days 2 or 3, and Days 5 or 8, and Weeks 4, 12, 16 or 20, 24, and 25
Secondary - Safety	
To evaluate the safety and tolerability of LYR-220	- Treatment-emergent adverse events (TEAEs) and serious adverse events (TESAEs) through Week 28
	- Clinically significant abnormal laboratory values (hematology and chemistry) through Week 25
	- Newly identified or worsened endoscopic findings (epistaxis and mucosal injury) in ethmoid cavity through Week 25
	- Clinically significant increase of IOP through Week 25
	A clinically significant increase of IOP is defined as IOP in 1 or both eyes >23 mm Hg or an increase of IOP from Baseline in one or both eyes \geq 10 mm Hg.
	- Newly identified or worsened cataract in 1 or both eyes by slit-lamp examination through Week 25
Secondary - Efficacy	
To evaluate the efficacy of LYR- 220 in improving total SNOT-22 and subdomain scores through	- Change from baseline (CFBL) in SNOT-22 total and subdomain scores at Weeks 2, 4, 6, 8, 12, 16, 20, 24, and 28
Week 28	The SNOT-22 questionnaire is a 22-item disease- specific quality of life instrument validated for use in CRS. Each symptom is scored as it has been over the past 2 weeks on a 6-point scale as follows: $0 = no$ problem, $1 = very$ mild problem, $2 = mild$ or slight

	problem, 3 = moderate problem, 4 = severe problem, 5 = problem as bad as it can be.
To evaluate the efficacy of LYR- 220 in improving 3CS and individual cardinal symptom score through Week 28	 CFBL in the average composite score over the preceding 7 days of 3 cardinal symptoms (3CS) and individual cardinal symptom scores at Weeks 2, 4, 6, 8, 12, 16, 20, 24, and 28
	The 3 cardinal symptoms include nasal blockage/obstruction/congestion, facial pain/ pressure, and anterior/posterior nasal discharge. Each symptom is scored on a 0-3 scale as follows: $0 = none$, $1 = mild$, $2 = moderate$, and $3 = severe$.

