8.3.11.5 Expectedness of Serious Adverse Events

The expectedness of a product or procedure related SAE should be determined by Sponsor based upon existing safety information about the investigation product or study procedure using these explanations:

- **Unexpected:** An SAE that is not listed in the study protocol, IB, or prescribing information for the registered formulation of MF or is not listed at the specificity or severity that has been observed.
- **Expected:** An SAE that is listed in the IB or prescribing information for the registered formulation of MF or is listed at the specificity and severity that has been observed.

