# 2 STUDY OVERVIEW

### 2.1 Study Objectives

#### 2.1.1 Primary Objective

The primary objective is to evaluate serious adverse events related to LYR-220.

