## 3.1.4 Endpoint Related Definition and Calculation

3.1.4.1 Product-Related Treatment-Emergent Serious Adverse Event (SAE)

Treatment-emergent adverse event is defined in Section 3.6.1.

A product-related treatment-emergent SAE must meet all the following criteria:

- 1. The treatment-emergent adverse event is serious.
- 2. The causality of an SAE is definitely related or possibly related to LYR-220 study drug product according to the investigator's assessment.
- 3.1.4.2 Newly Identified or Worsened Endoscopic Findings (Epistaxis and Mucosal Injury) in Ethmoid Cavity through Week 25/Follow Up

A newly identified endoscopic finding in ethmoid cavity is a development of epistaxis or mucosal injury at post-baseline visits.

A worsened endoscopic finding in ethmoid cavity is an increased severity change of either epistaxis or mucosal injury from baseline.

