# 5 CHANGES FROM PROTOCOL-SPECIFIED STATISTICAL ANALYSES

There is no change from the protocol-specified statistical analyses.

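### The SAP's primary endpoint omits expectedness and adds a treatment-emergent window, so the protocol's primary result cannot be read as its own category

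*SAP*

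**What the plan says.** **Protocol.** Section 3 gives the primary objective as "To evaluate unexpected serious adverse events related to LYR-220" and the primary endpoint as "Product-related unexpected serious adverse events". The synopsis gives the same endpoint. Section 8.3.11.5 makes the term operational: "The expectedness of a product or procedure related SAE should be determined by Sponsor based upon existing safety information". An SAE counts as unexpected if the reference safety documents do not list it, or do not list it at the specificity or severity observed.

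**SAP.** Section 2.1.1 states "The primary objective is to evaluate serious adverse events related to LYR-220". Section 2.3.1 states "The primary endpoint is product-related treatment-emergent serious adverse events (TESAEs". Section 3.1.4.1 begins "A product-related treatment-emergent SAE must meet all the following criteria" and then gives two conditions: the treatment-emergent event is serious, and the investigator rates it definitely or possibly related to the product. Section 3.6.1 limits treatment-emergent events to those starting after treatment administration begins and no later than 31 days after treatment is discontinued.

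**Outputs.** SAP 3.6.1 plans an overview, tables by system organ class and preferred term for the overview categories, and a listing of product-related TESAEs. SAP 4.2 (Primary Lock Analysis) adds a table of product-related TESAEs by system organ class and preferred term. None of these uses expectedness. SAP Section 5 states "There is no change from the protocol-specified statistical analyses".

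**The concern.** A primary endpoint should carry the same definition from protocol to SAP to report. Here one defining condition is dropped and another is added, and Section 5 records neither. Someone following the SAP would report a count that mixes expected and unexpected related SAEs under the primary-endpoint label, and could not recover the protocol's figure from any specified table or listing.

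Expectedness is also part of what sets the protocol's primary endpoint apart. TESAEs of every kind are already a secondary safety endpoint in both documents. Without the expectedness condition, the primary endpoint is simply the product-related subset of that secondary one.

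Timing matters too. SAP 4.2 treats changes made after the Primary Lock Analysis as post hoc, so the definition is better settled in the SAP than repaired in the study report.

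**Working it through.** The plan states no figure to reproduce: the sample size is not power-based and no safety test is planned. The check is a comparison of definitions followed by a small illustration.

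**1. Conditions for an event to count**

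| Condition | Protocol Section 3 | SAP 2.3.1 and 3.1.4.1 |
|---|---|---|
| Serious | yes | yes |
| Product-related | yes | yes (definitely or possibly, per investigator) |
| Unexpected | yes (sponsor, 8.3.11.5) | not required |
| Treatment-emergent, up to 31 days after discontinuation | not stated | yes (3.6.1) |

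The SAP removes one condition and adds one, so neither endpoint strictly contains the other. The removal can only add expected events. The addition can only exclude late ones. The second effect should be small: a product-related event must follow administration anyway, and the protocol schedules the end-of-study contact 25 to 31 days after end of treatment.

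**2. Where a treatment-emergent unexpected related SAE would appear**

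It meets both SAP conditions, so it enters the product-related TESAE listing (3.6.1) and the Primary Lock table (4.2). Neither carries an expectedness field, so it cannot be told apart there from an expected event.

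**3. Whether the SAP's own endpoint is tabulated at the final analysis**

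The overview in 3.6.1 lists product-related TEAEs and all TESAEs as separate categories. Their combination, product-related TESAEs, is specified there only as a listing. The explicit table appears only in the Primary Lock list, so the final analysis has no such row to extend.

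**4. Illustrative size**

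Inputs:
- Part 2 plans about 20 subjects per arm (protocol synopsis; SAP 2.2.1).
- Part 1 treats up to 10 subjects with either design (same sections).
- SAP 3.1 pools LYR-220-32 subjects from both parts for safety.

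The pooled LYR-220-32 denominator is 20 + k, where k is the number of Part 1 subjects given that design, between 0 and 10. That gives about 20 to 30.

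Suppose one subject has one related, expected, treatment-emergent SAE and there are no other related SAEs:
- Protocol endpoint: 0/20 to 0/30 = 0%.
- SAP endpoint: 1/20 = 5.0% down to 1/30 = 3.3%.

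If no related SAE occurs, both endpoints are 0%.

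**The case against.** Five points can be made for the SAP.

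*The wider count is conservative.* Dropping the expectedness restriction cannot hide an unexpected event. A reader might infer that unexpected related SAEs would have no table or listing at all. The documents do not support that: the treatment-emergent ones sit inside the listing and the Primary Lock table. What is missing is the label that separates them. This narrows the point but does not remove it, because the protocol's primary result still cannot be read.

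*The output gap starts in the protocol.* Protocol 9.6 names no table by expectedness either, so the SAP did not delete a specified output, and Section 5 speaks of analyses. That stands as far as outputs go. The changed objective and endpoint definition are the SAP's own.

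*The change may be declared elsewhere.* The SAP contents page lists an Appendix E summarising changes from the protocol, but its text is not available. A reader might infer an undisclosed redefinition; that cannot be established. If Appendix E does record the change, it conflicts with Section 5, and the definitions still differ.

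*The illustration may never arise.* It needs a related SAE that is also expected. The Investigator's Brochure and prescribing information are not available, so its likelihood is unknown. Protocol Section 11 describes the most common treatment-related events in the earlier LYR-210 studies as nonserious. This is fair, but a prespecified endpoint should not depend on the event being absent.

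*Nothing is decided on this endpoint.* There is no safety test and no decision rule tied to it. A reader might infer that subject safety reporting is weakened. It is not: SAE, SUSAR and UADE reporting under protocol 8.3.11.6 is unaffected.

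**Conclusion.** The point holds as a mismatch in the primary endpoint's definition. SAP 2.1.1, 2.3.1 and 3.1.4.1 omit the expectedness condition, the SAP adds a treatment-emergent window, and no specified output separates related SAEs by expectedness. Section 5 nevertheless reports no change.

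The size is modest. On the assumption of a single related but expected SAE, the LYR-220-32 result moves from 0% to about 3.3% to 5%, depending on how many Part 1 subjects received that design. The conclusion rests on the definitions and not on that example. It is subject to one gap, the unseen Appendix E, which could alter what has been declared but not what has been defined.

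**What to change.** 1. Restore *unexpected* in SAP 2.1.1, 2.3.1 and 3.1.4.1, using the sponsor's classification under protocol 8.3.11.5 as a third criterion.
2. Bring that classification into the analysis data. The AE and initial SAE report items listed in protocol 8.3.11.6 do not include expectedness, so it should not be assumed to exist there already.
3. Add to the final analysis a short by-treatment table of product-related unexpected SAEs, with all product-related TESAEs as the next row. This keeps the wider count and gives the final analysis an explicit table for it.
4. In Section 5, state the treatment-emergent restriction and any other remaining difference from the protocol, and make it agree with Appendix E.

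If the sponsor prefers the wider endpoint, the alternative is to amend the protocol and declare the change in Section 5.

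The cost is one short table and one added variable. The sponsor already has to make the classification, so no new clinical data are needed.

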# 2.3.2 Secondary Safety Endpoints

The secondary safety endpoints include:

- 1. Treatment-emergent adverse events (TEAEs) and serious adverse events through Week 28/Follow Up.
- 2. Clinically significant abnormal laboratory values (hematology and chemistry) through Week 25/Follow Up.
- 3. Newly identified or worsened endoscopic findings (epistaxis and mucosal injury) in ethmoid cavity through Week 25/Follow Up.
- 4. Clinically significant increase of IOP through Week 25/Follow Up.
- 5. Newly identified or worsened cataract in 1 or both eyes by slit-lamp examination through Week 25/Follow Up.

## 2.3.3 Secondary Efficacy Endpoints

The secondary efficacy endpoints are:

- 1. Change from baseline (CFBL) in SNOT-22 total and subdomain scores at Weeks 2, 4, 6, 8, 12, 16, 20, 24, and 28/Follow Up.
- 2. CFBL in the 7-day average composite score of 3CS and individual cardinal symptom scores at Weeks 2, 4, 6, 8, 12, 16, 20, 24, and 28/Follow Up.
- 3. CFBL in the 7-day average score of loss of smell for subjects with baseline score ≥2 at Weeks 2, 4, 6, 8, 12, 16, 20, 24, and 28/Follow Up.
- 4. CFBL in CRS-PRO total and subdomain scores at Weeks 2, 3, 4, 6, 8, 12, 16, 20, 24, and 28/Follow Up.
- 5. Time to first rescue treatment recommendation through Week 28/Follow Up.
- 6. Systemic/oral corticosteroid use or sinonasal surgery recommendation through Week 28/Follow Up.
- CFBL in bilateral percent ethmoid cavity opacification by CT at Week 25/Follow Up.
- 8. CFBL in PGIS score at Weeks 8, 16, and 24.
- 9. PGIC score at Week 24.
- 10. No longer a candidate for revision surgery.
- 11. CFBL in nasal inflammatory marker levels at Week 25/Follow Up.

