To evaluate the efficacy of LYR- 220 in improving loss of smell symptom score through Week 28 for subjects with moderate-to- severe score at baseline	 CFBL in average loss of smell score over the preceding 7 days for all subjects and subjects with baseline score ≥2 at Weeks 2, 4, 6, 8, 12, 16, 20, 24, and 28
To evaluate the efficacy of LYR- 220 in improving total Patient- Reported Outcome Measure for Chronic Rhinosinusitis (CRS-	 Change from baseline (CFBL) in Patient-Reported Outcome Measure for Chronic Rhinosinusitis (CRS-PRO) total and subdomain scores at Day 8 and Weeks 2, 3, 4, 6, 8, 12, 16, 20, 24, and 28
PRO) and subdomain scores through Week 28	The CRS-PRO questionnaire is a 12-item disease- specific health-related impairment for use in CRS. Each symptom is scored as it has been over the past 7 days on a 5-point scale as follows: $0 = not$ at all, $1 = a$ little bit, 2 = somewhat, $3 = quite a bit$, $4 = very much$.
To evaluate the time to first rescue treatment recommendation	- Time to first rescue treatment recommendation through Week 28
through Week 28	Rescue treatment is defined as, after subject enrollment, worsening or acute exacerbation of CRS in a subject resulting in the treating physician reporting an escalation of treatment, including systemic corticosteroids (SCS), and/or sinonasal surgery. Rescue treatment is not recommended if worsening of symptoms is for less than 3 days duration.
To evaluate the percentage of subjects who have uncontrolled CRS symptoms requiring oral	 Oral steroid use or sinonasal surgery recommendation through Week 28

steroids or sinonasal surgery through Week 28	
To evaluate the effect of LYR-220 in reducing ethmoid cavity opacification as per CT	 CFBL in bilateral percent ethmoid cavity opacification by CT at Week 25
To evaluate the efficacy of LYR- 220 in improving subject perception of symptom severity and improvement	 CFBL in the Patient Global Impression of Severity (PGIS) score at Weeks 8, 16, and 24 Patient Global Impression of Change (PGIC) score at Week 24
To evaluate the effect of LYR-220 in converting a subject to not requiring revision surgery	 No longer a candidate for revision surgery Subjects will be deemed as having converted if they do not undergo revision sinonasal surgery (planned or actual) during the study and if they meet the following criteria: 3CS score ≤4 at Week 24, or No disease in ethmoid cavities on Week 25 CT

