Ophthalmologic assessments will include intraocular pressure (IOP) and slit-lamp examination during Screening and at Week 25/Follow Up visit. IOP assessment will also be performed at Week 4 and 12 visits.

For female subjects of childbearing potential, a serum pregnancy test will be performed at the Screening visit and a urine pregnancy test will be performed on Day 1 prior to treatment to confirm eligibility for participating in the study. Additionally, a urine pregnancy test will be performed at Weeks 4, 12, and 24 or early termination (ET) visits in these female subjects.

Plasma samples for pharmacokinetics (PK) will be collected from all subjects at Day 1 preprocedure, 1 hour (±10 minutes) post procedure on Day 1, Day 2 or 3, Day 5 or 8, and Weeks 4, 12, 16 or 20, 24, and Week 25/Follow Up visits.

Enrolled subjects will be asked to complete a daily electronic patient-reported outcomes (ePRO) questionnaire to assess the severity of the 4 CS of CRS (nasal blockage/obstruction/congestion, facial pain/pressure, anterior/posterior nasal discharge, and loss of smell). In addition, the ePRO will capture use of daily saline irrigation by the subjects. Subjects will also complete 2 validated CRS-specific quality of life questionnaires, the SNOT-22 and CRS-PRO, at Screening, on Day 1 before treatment, and at Weeks 2, 4, 6, 8, 12, 16, and 20, at Week 24 before matrix removal, and at Week 28/Follow Up. CRS-PRO will also be assessed at Day 8 and Week 3. The Patient Global Impression of Severity (PGIS) will be administered on Day 1 (pretreatment) and at Weeks 8, 16, and 24. The Patient Global Impression of Change (PGIC) will be assessed at Week 24. At Week 28/Follow Up visit, an end-of-study questionnaire will be administered.

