### 3.1.1 Analysis Day

Analysis day for analysis visit windows (i.e., "Aday") will be calculated from the date of study treatment (LYR-220 or sham) administration. The day of study treatment administration will be Aday 1, and the day immediately before Aday 1 will be Aday -1.

Additionally, analysis day relative to the last dose day (i.e., "Aenday") will be calculated from the date of last dose of study treatment. The day of last dose of study treatment will be Aenday 0, and the day immediately after Aenday 0 will be Aenday 1. Data collected up to 31 days after end of treatment will be included in the analysis.

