# 3.1.2.1 Analysis Visit Windows for Efficacy Endpoints

Table 1a. Visit Windows for SNOT-22

Analysis Visit	Target Analysis Day	Low Analysis Day	High Analysis Day
Week 2	Aday 15	Aday 2	Aday 21
Week 4	Aday 29	Aday 22	Aday 35
Week 6	Aday 43	Aday 36	Aday 49
Week 8	Aday 57	Aday 50	Aday 70
Week 12	Aday 85	Aday 71	Aday 98
Week 16	Aday 113	Aday 99	Aday 126
Week 20	Aday 141	Aday 127	Aday 154
Week 24	Aday 169	Aday 155	Aday 182
Week 28/follow-up*	Aenday 28	Aenday 1	Aenday 31

\* post-treatment follow-up.

Table 1b. Visits for Weekly 3CS and 4 Individual Cardinal Symptom Scores

Analysis Visit	Analysis Week (Days)
Week 1	Aday 2 - Aday 8
Week 2	Aday 9 - Aday 15
Week 3	Aday 16 - Aday 22
Week 4	Aday 23 - Aday 29
Week 5	Aday 30 - Aday 36
Week 6	Aday 37 - Aday 43
Week 7	Aday 44 - Aday 50
Week 8	Aday 51 - Aday 57
Week 9	Aday 58 - Aday 64
Week 10	Aday 65 - Aday 71
Week 11	Aday 72 - Aday 78
Week 12	Aday 79 - Aday 85
Week 13	Aday 86 - Aday 92
Week 14	Aday 93 - Aday 99
Week 15	Aday 100 - Aday 106
Week 16	Aday 107 - Aday 113
Week 17	Aday 114 - Aday 120
Week 18	Aday 121 - Aday 127
Week 19	Aday 128 - Aday 134
Week 20	Aday 135 - Aday 141
Week 21	Aday 142 - Aday 148
Week 22	Aday 149 - Aday 155

Week 23	Aday 156 - Aday 162	
Week 24	Aday 163 - Aday 169	
Week 25/follow-up*	Aenday 1 - Aenday 7	
Week 26/follow-up*	Aenday 8 - Aenday 14	
Week 27/follow-up*	Aenday 15 - Aenday 21	
Week 28/follow-up*	Aenday 22 - Aenday 28	

Note: score for a week is the average of the non-missing daily scores over the 7-day period of the week. If less than 4 daily scores are available for a week, the individual CS score will be considered missing for that week.

Table 1c. Visit Windows for CRS-PRO

Analysis Visit	Target Analysis Day	Low Analysis Day	High Analysis Day
Week 2	Aday 15	Aday 12	Aday 18
Week 3	Aday 22	Aday 19	Aday 25
Week 4	Aday 29	Aday 26	Aday 35
Week 6	Aday 43	Aday 36	Aday 49
Week 8	Aday 57	Aday 50	Aday 70
Week 12	Aday 85	Aday 71	Aday 98
Week 16	Aday 113	Aday 99	Aday 126
Week 20	Aday 141	Aday 127	Aday 154
Week 24	Aday 169	Aday 155	Aday 182
Week 28/follow-up*	Aenday 28	Aenday 1	Aenday 31

\* post-treatment follow-up.

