3.4.2.3 CFBL in CRS-PRO at Weeks 2, 3, 4, 6, 8, 12, 16, 20, 24, and 28/Follow-up 3.4.2.3.1 Part 1

Descriptive summary statistics on the values and changes from baseline will be presented at each analysis visit by treatment group.

# 3.4.2.3.2 Part 2

CRS-PRO subdomain scores will be summarized descriptively without formal statistical test.

Descriptive summary statistics on the values and changes from baseline will be presented for CRS-PRO total and subdomain scores at each analysis visit by treatment group.

The estimands attributes for CRS-PRO are defined in the same manner as for "CFBL in SNOT-22 Total and Subdomain Scores" in Section 3.4.2.1.1. Missing data will not be imputed. The same MMRM analysis method used for the SNOT-22 total and subdomain scores will be used for CRS-PRO total score. The LS-means for change from baseline at each analysis visit will be provided for each treatment group and the difference between LYR-220 and sham treatment at each analysis visit will be estimated along with the CIs. The p-value for the comparison at each analysis visit will also be presented.

## 3.4.2.4 CFBL in PGIS at Weeks 8, 16, and 24

#### 3.4.2.4.1 Part 1

Descriptive summary statistics on the values and changes from baseline will be presented at each analysis visit by treatment group.

#### 3.4.2.4.2 Part 2

The estimands attributes are defined in the same manner as for "CFBL in SNOT-22 Total and Subdomain Scores" in Section 3.4.2.1.1. Missing data will not be imputed. The same MMRM analysis method used for the SNOT-22 total and subdomain scores will be used. The LS-means for change from baseline at each analysis visit will be provided for each treatment group and the difference between LYR-220 and sham treatment at each analysis visit will be estimated along with the CIs. The p-value for the comparison at each analysis visit will also be presented.

Descriptive summary statistics on the values and changes from baseline will be presented for the above secondary efficacy endpoints at each analysis visit by treatment group.

3.4.2.5 Time-to-First Recommendation of Rescue Treatment through Week 28/Follow-up 3.4.2.5.1 Part 1

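### CRS-PRO at Day 8 is a protocol secondary endpoint time point and is collected, but the SAP gives it no analysis visit, so it is normally listed and not analysed

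*SAP*

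**What the plan says.** **Protocol.** Section 3 (and the synopsis) sets the CRS-PRO endpoint as change from baseline in "total and subdomain scores at Day 8 and Weeks 2, 3, 4, 6, 8, 12, 16, 20, 24, and 28". Section 8.1 and its Table 1 schedule the questionnaire on Day 8. Section 9.8.1.1 plans by-timepoint descriptive statistics and an MMRM for CRS-PRO, and makes no exception for Day 8.

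**SAP, collection.** Section 2.2.1 agrees with the protocol: "CRS-PRO will also be assessed at Day 8 and Week 3".

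**SAP, endpoint and analysis.** Section 2.3.3 item 4 lists "CFBL in CRS-PRO total and subdomain scores at Weeks 2, 3, 4, 6, 8, 12, 16, 20, 24" and the Week 28 follow-up. Section 3.4.2.3 is headed "CFBL in CRS-PRO at Weeks 2, 3, 4, 6, 8, 12, 16, 20, 24, and 28/Follow-up". Day 8 is in neither.

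**SAP, windows.** Section 3.1.1 fixes the day count: "The day of study treatment administration will be Aday 1". In Section 3.1.2.1, under "Table 1c. Visit Windows for CRS-PRO", the first row is "Week 2 Aday 15 Aday 12 Aday 18". Section 3.1.2 treats a scheduled visit outside its window as unscheduled. If no window fits, the record stays in the database and goes into the listings.

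**SAP, departures.** Section 5 declares no change from the protocol's statistical analyses.

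**The concern.** The two documents agree that the score is collected on Day 8 but disagree on whether it is an endpoint time point. Followed as written, the SAP leaves a protocol-specified time point out of every by-visit table and out of the model, and the section meant to record departures says there are none.

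Day 8 is the only change-from-baseline efficacy time point that the protocol places before Week 2. SNOT-22, the cardinal symptoms and loss of smell start at Week 2, and PGIS at Week 8. With its 7-day recall, a Day 8 CRS-PRO describes the first week after the procedure. If the gap is noticed late, it also becomes harder to repair. SAP 4.2 classes changes made after the primary lock analysis as post hoc, so a time point that the protocol prespecified would then carry that label.

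**Working it through.** The plan gives no figure to reproduce, because the sample size does not rest on power. The check sets the two lists side by side and maps Day 8 onto the windows.

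**1. Time points**

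| Source | Post-baseline CRS-PRO time points | Count |
|---|---|---|
| Protocol Section 3 | Day 8; Weeks 2, 3, 4, 6, 8, 12, 16, 20, 24, 28 | 11 |
| SAP 2.3.3 item 4 and 3.4.2.3 | Weeks 2, 3, 4, 6, 8, 12, 16, 20, 24, 28 | 10 |

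The only difference is Day 8. Week 3, the other time point used for CRS-PRO but not for SNOT-22, is kept throughout the SAP.

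**2. Windows.** Treatment day is Aday 1, so protocol Day 8 is Aday 8. The on-treatment windows in Table 1c are:

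| Visit | Window (Aday) |
|---|---|
| Week 2 | 12–18 |
| Week 3 | 19–25 |
| Week 4 | 26–35 |
| Week 6 | 36–49 |
| Week 8 | 50–70 |
| Week 12 | 71–98 |
| Week 16 | 99–126 |
| Week 20 | 127–154 |
| Week 24 | 155–182 |

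They run without a gap from Aday 12 to Aday 182. Aday 2 to Aday 11 belongs to no window, and Aday 8 lies inside that gap.

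**3. The one other route.** The Week 28/follow-up window takes Aenday 1 to 31, counted from the end of treatment. If treatment ends on Aday e, a Day 8 record has Aenday = 8 − e. This is at least 1 only when e ≤ 7. So only a subject whose treatment ended on Aday 1 to 7 could have a Day 8 score enter an analysis visit. It would then be labelled follow-up, and would give way to any record in that window nearer the target of Aenday 28.

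**4. Number of records.** Part 2 plans about 40 subjects, so at most about 40 Part 2 records are affected, if every subject completes the Day 8 questionnaire. Part 1 adds up to 10, which would be summarised descriptively.

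**5. Which window would suit Day 8.** The neighbouring windows are the target ± 3 days (15 ± 3 = 12–18; 22 ± 3 = 19–25). The same rule gives 8 ± 3 = Aday 5–11, which meets the Week 2 window without overlap.

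Filling the whole gap (Aday 2–11) would be worse because of the recall period. The SAP has no day 0, so for a record on Aday d (d ≤ 8) the 7 preceding days include d − 1 days from treatment day onward:
- Aday 2: 1 of 7 days
- Aday 5: 4 of 7 days
- Aday 8: 7 of 7 days

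**6. Cost to the model.** An unstructured covariance for k visits has k(k + 1)/2 parameters. For k = 10 this is 10 × 11 / 2 = 55. For k = 11 it is 11 × 12 / 2 = 66. Adding Day 8 therefore costs 11 parameters with about 40 subjects.

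**The case against.** Five fair points can be made for the SAP.

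- **Nothing is discarded.** A reader might infer that all Day 8 data are thrown away. The documents do not support that. Under SAP 3.1.2 the CRS-PRO records stay in the database and the listings, and other Day 8 data (cardinal symptoms, PK) have their own place.
- **Day 8 is not the only evidence on onset.** A reader might also infer that early-onset evidence is lost. The cardinal symptoms are rated daily, and SAP Table 1b defines a Week 1 visit (Aday 2–8) for the 3CS and all four symptoms. The qualification is that Week 1 is not an endpoint time point in SAP 2.3.3 or in the heading of 3.4.2.2. Section 3.4.2.2 does, however, promise descriptive summaries at each analysis visit.
- **The omission may be recorded elsewhere.** The SAP contents page lists an Appendix E on changes from the protocol, and its text was not available. The charge that the omission is undeclared anywhere therefore cannot be made. What stands is that Section 5, as worded, does not match the protocol for this endpoint.
- **The stakes are low.** The endpoint is secondary and unpowered, there is no multiplicity control, and CRS-PRO is not among the primary lock outputs. No estimate at another visit has been shown to be biased.
- **Completeness is unknown.** Subjects attend the clinic on Day 5 or Day 8, so some will not be on site on Day 8. Completion by ePRO away from the clinic is possible, but the yield cannot be known in advance.

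All five limit the size of the point. None explains why the SAP collects the score on Day 8 and gives it no analysis visit.

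**Conclusion.** The inconsistency is real and visible in the text. A protocol-named secondary endpoint time point is missing from the SAP's endpoint list, window table and analysis section. Its records normally reach listings only, and Section 5's statement is incorrect for this endpoint.

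The size is modest: one of 11 CRS-PRO time points and at most about 40 Part 2 records. The primary safety endpoint and the other CRS-PRO visits keep their planned analyses.

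The conclusion rests on two readings. First, Aenday is taken to count from the end of treatment (removal or loss of the matrices, or sham removal), as the follow-up labels in Section 3.1.2 imply. Second, Section 5 is taken at face value; Appendix E might record the change, but Section 5 would then contradict it. Whether the omission was an oversight is not stated. The retention of Week 3, and a Week 2 window that starts just where a Day 8 window would end, are consistent with a dropped row but do not prove one.

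**What to change.** 1. Add a Day 8 row to Table 1c: target Aday 8, low Aday 5, high Aday 11. This matches the ± 3 days of the Week 2 and Week 3 windows. Scores from the early edge will still recall up to 3 pre-treatment days.
2. Restore Day 8 in SAP 2.3.3 item 4 and in 3.4.2.3.
3. Report Day 8 in the by-visit descriptive tables for total and subdomain scores, and include it as a visit in the CRS-PRO total-score MMRM.
4. If the removal was intended, state and justify it in Section 5, and make sure Appendix E agrees.

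The cost is one table row, two text edits and one more visit. The statistical downside is the rise from 55 to 66 covariance parameters, which makes the prespecified fallback to heterogeneous Toeplitz or compound symmetry more likely. If that is a worry, give Day 8 descriptively and keep it out of the model. The change is best made before the primary lock analysis; under SAP 4.2 a later one that affects the analysis would be labelled post hoc.
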